#### **6.8.5. Vital Signs and Other Physical Findings**

The frequency and percentage of patients meeting any of the potentially clinically significant abnormality criteria (defined in [Appendix Table 4](#)) at any time point post-baseline will be summarized by Analysis Period and treatment group as defined in Section 5.1. Additionally, the total number of potentially clinically significant abnormalities will be summarized.

Baseline value, highest/largest absolute change and last observation and the corresponding change from Baseline will be summarized by analysis period and treatment group. The largest absolute change from Baseline will be summarized for systolic blood pressure, diastolic blood pressure, and respiratory rate, and the highest value for pulse and temperature. If the largest absolute change from Baseline occurs in

both directions equally, then the higher value will be summarized. The highest/largest absolute change value will not be summarized for height, weight, BMI, ulnar length, or calculated height. Only results that occurred within 28 days of the last dose of study drug, or before initiation of a new study drug will be included.

Vital signs will be listed for all patients. In addition, values meeting the potentially clinically significant criteria will be presented in a data listing. Treatment-emergent abnormalities will be indicated. Height and weight will also be listed.

[figure not shown]

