An ECG will be performed at Screening, Baseline/Week 1, Week 7, Week 12, and, then every 12 weeks. An ECHO will be performed at Screening, Week 12, and, then every 24 weeks. Clinical laboratory assessments will be performed at Screening, Baseline/Week 1, Weeks 2-9, Week 12, then, every 4 weeks to Week 36, and, then every 12 weeks. Vital signs will be assessed weekly pre- and post-infusion. Height will be assessed at Screening and, then, every 12 weeks. Weight will be assessed at Screening, Baseline/Week 1, and, then, every 4 weeks. A full physical exam will be conducted at Screening, Baseline/Week 1, Week 4, Week 12, Week 24, and, then, every 24 weeks. A brief physical exam will be conducted every 4 weeks (except at times of a full physical exam) to Week 36 and, then, every 24 weeks.

Additional safety assessments will be performed during the first 8 weeks of open-label treatment, as specified in the Schedule of Events ([Table 3](#)).

[figure not shown]
All assessments are specified in the Schedule of Events ([Table 2](#) and [Table 3](#)). [Figure 1](#) is a schematic of the study design.

Figure 1: Study Design Schematic

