7.3. Study Endpoints

The following study endpoints will be evaluated in this study. Descriptions of all study assessments and procedures are provided in Section 10.

The primary endpoint is assessment of the safety of SRP-4045 during the double-blind dose-titration period according to the following:

- Incidence of AEs

- Incidence of clinical laboratory abnormalities (hematology, chemistry, coagulation, urinalysis)
- Incidence of abnormalities in vital signs and physical examinations
- Clinically significant worsening of ECGs and ECHO

The secondary endpoint is to determine the PK profile of SRP-4045 during the double-blind dose-titration period:

[figure not shown]
- Maximum plasma concentration (C_{max})
- Time to maximum plasma concentration (T_{max})
- Area under the plasma concentration-curve (AUC)
- Apparent volume of distribution at steady state (V_{ss})
- Elimination half-life ($t_{1/2}$)
- Total clearance (CL)
- Mean residence time (MRT)
- Urinary clearance (CL_R)

CCI

[figure not shown]

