10.3. Safety Assessments

10.3.1. Vital Signs including Weight and Height

Vital signs including oral temperature, heart rate, respiratory rate and blood pressure as well as height and weight will be measured at the time points specified in the schedule of events (Table 2).

For infusion visits, vital signs are to be collected within approximately 30 minutes prior to the start of the infusion, and approximately 5, 30, and 60 minutes after the end of the infusion (ie, after investigational product has been flushed through the IV line). If the patient has not experienced an infusion reaction after 48 weeks of open-label treatment, collect vital signs prior to infusion and at 5 and 30 minutes post-infusion.

Vital signs will be performed after patients have remained seated for 5 minutes. Pulse rate and respiratory rate are to be measured over 1 minute.

Temperature is to be reported in degrees Celsius (°C).

Weight is to be reported in kilograms. If a patient's weight varies by more than 10% from the prior visit, the patient is to be re-weighed to confirm the result, and an explanation of the change must be documented.

Height is to be measured with shoes off. Ulna length should be collected measured when height is obtained for all patients. If standing height cannot be obtained, height is to be calculated using the following equation (Gauld 2004) for entry into the spirometry system:

$$\text{Height (cm)} = 4.605U + 1.308A + 28.003$$

where U is the length of the ulna in centimeters measured using an anthropometer or calipers, and A is the patient's age in years.

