**Appendix Table 4 Vital Sign Abnormalities of Interest**

Variable	Units	Markedly Abnormal Criteria Lower limit	Markedly Abnormal Criteria Upper limit
Systolic blood pressure	mmHg	<80	>130
Diastolic blood pressure	mmHg	<40	>90
Pulse Rate	beats/minute	<50	>130
Respiratory Rate	breaths/min	<12	>20
Temperature	°C	<36.0	>38.0
Weight	kg	Decrease of 7% or more	NA

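### The any-reading vital-sign abnormality percentage rises with the number of readings in a column, so whole-period placebo and the shorter dose columns are not like-for-like

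*SAP*

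**What the plan says.** Protocol 7.3 lists "Incidence of abnormalities in vital signs and physical examinations" as a component of the primary safety endpoint for the double-blind period.

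**Counting rule.** SAP 6.8.5 gives the number and percentage of patients who meet a criterion "at any time point post-baseline will be summarized by Analysis Period and treatment group as defined in Section 5.1". It then says: "Additionally, the total number of potentially clinically significant abnormalities will be summarized". No confirmation by a second reading is required.

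**Criteria.** Appendix Table 4 has a column headed "Markedly Abnormal Criteria Lower limit" and a matching upper limit. Blood pressure (systolic and diastolic), pulse, respiratory rate and temperature have fixed limits with no reference to baseline. Only weight has a change criterion, a fall of at least 7%.

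**Reading schedule.** Protocol 7.1 states: "Vital signs will be assessed weekly pre- and post-infusion". Protocol 10.3.1 gives the times: "vital signs are to be collected within approximately 30 minutes prior to the start of the infusion, and approximately 5, 30, and 60 minutes" after it ends, which makes four readings per visit. After 48 open-label weeks without an infusion reaction, the instruction is to "collect vital signs prior to infusion and at 5 and 30 minutes post-infusion", which makes three.

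**Columns.** For the double-blind period, SAP 5.1 lists placebo (whole period), the four titration steps, ≤20 mg/kg in Weeks 1-6 (select endpoints only), 30 mg/kg from Week 7 to the end, and any-dose casimersen (whole period). The Casimersen Period has a single group. The Protocol synopsis also says that vital-sign abnormalities will be tabulated by dose and treatment group.

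**The concern.** The chance that a patient has at least one reading beyond a fixed limit grows with the number of readings he has. The columns planned for the same table cover 2, 6, about 10 and about 16 weeks, so equal risk per reading gives unequal percentages. Placebo is in one of the longest columns, so the distortion runs in the direction that could hide a drug effect at a given dose.

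Counting patients who were already beyond a limit at baseline adds noise that has nothing to do with treatment. In arms this small it matters: one placebo patient is 1/4 = 25 percentage points and one casimersen patient is 1/8 = 12.5.

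**Working it through.** The documents give no expected abnormality rate, so there is no stated figure to reproduce. The check counts readings from the schedule and then applies assumed rates.

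**Readings per patient.** The first pre-infusion reading is the baseline (SAP 5.8), so one is subtracted where a column starts at the first dose.

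- 4 mg/kg, Weeks 1-2: 2 × 4 − 1 = 7. Each later 2-week step: 2 × 4 = 8.
- ≤20 mg/kg, Weeks 1-6: 6 × 4 − 1 = 23.
- 30 mg/kg, Weeks 7-16: 10 × 4 = 40.
- Placebo or any-dose casimersen, 16 weeks: 16 × 4 − 1 = 63. Sixteen weeks is the approximate length for the last patient enrolled (SAP 4.3.2); earlier patients stay blinded for longer.
- Casimersen Period, casimersen-first: 144 × 4 − 1 = 575, or 64 × 4 + 80 × 3 − 1 = 495 with the reduced schedule.
- Casimersen Period, placebo-first (about 128 open-label weeks): 128 × 4 − 1 = 511, or 48 × 4 + 80 × 3 − 1 = 431.

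**Formulas.** Let p be the chance that one reading crosses a limit (assumed, and the same in every column).

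- Independent readings: P(at least one in n) = 1 − (1 − p)^n.
- Correlated readings: a beta-binomial with intraclass correlation (ICC) ρ, a = p(1 − ρ)/ρ and b = (1 − p)(1 − ρ)/ρ. Then P = 1 − Π (b + i)/(a + b + i) for i = 0 to n − 1. At p = 1% and ρ = 0.1 (assumed), a = 0.09 and b = 8.91.

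**Results.**

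| Column | n | p = 0.1%, indep. | p = 0.5%, indep. | p = 1%, indep. | p = 2%, indep. | p = 1%, ICC 0.1 |
|---|---|---|---|---|---|---|
| 2-week step | 8 | 0.8% | 3.9% | 7.7% | 14.9% | 5.8% |
| ≤20 mg/kg | 23 | 2.3% | 10.9% | 20.6% | 37.2% | 11.1% |
| 30 mg/kg, Weeks 7-16 | 40 | 3.9% | 18.2% | 33.1% | 55.4% | 14.5% |
| Placebo or any-dose casimersen | 63 | 6.1% | 27.1% | 46.9% | 72.0% | 17.5% |
| Casimersen Period | 495 | 39.1% | 91.6% | 99.3% | about 100% | 30.8% |

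For example, 1 − 0.99^8 = 7.7% and 1 − 0.99^63 = 46.9%. The same 30 mg/kg dose shows 7.7% or 33.1%, depending only on whether its column stops at Week 8 or runs to Week 16.

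The ratio of the 63-reading to the 8-reading column at p = 1% is 46.9/7.7 = 6.1 under independence and 17.5/5.8 = 3.0 at ICC 0.1. Stronger correlation shrinks it: at ICC 0.5 the figures are 2.7% and 4.6%.

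**One reading of the rule makes it larger.** SAP 6.8.5 can be read as counting each criterion separately or as one composite. With a composite over five signs, each independent at 0.5% per reading, the per-reading chance is 1 − 0.995^5 = 2.5%. The percentages become 18.2% (8 readings) and 79.4% (63).

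**The case against.** **The main randomised comparison is sound.** A reader might infer that the primary safety comparison is biased against placebo. The documents do not support that. SAP 5.1 includes any-dose casimersen over the whole double-blind period, with the same weekly schedule and length as placebo. Reading count creates no systematic bias there, although patients enrolled early contribute more readings and chance could spread them unevenly between arms of 4 and 8.

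**Saturation is not established.** A reader might also infer that the measure climbs to nearly 100% and cannot separate groups. Near-100% figures arise only in the Casimersen Period, which has one treatment group and lies outside the double-blind primary endpoint. They also need near-independent readings and an assumed risk of about 0.5-1% or more. At 1% with ICC 0.1 the figure is about 31%, and readings minutes apart in one patient are unlikely to be independent.

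**Baseline is not ignored throughout.** Weight has a change criterion, and SAP 6.8.5 flags treatment-emergent values in the listing.

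**The short columns may not all appear.** ≤20 mg/kg is for select endpoints, the titration bullet could mean one column or four, and 6.8.5 does not say by dose level as the adverse event sections do. That is fair. However, 30 mg/kg from Week 7 onward is listed without qualification, and the Protocol synopsis asks for tabulation by dose.

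**Other outputs help, but only in part.** With 12 patients, individual review is feasible and the analysis is descriptive. But the total number of abnormalities has no denominator, and the highest value and largest change also grow with the number of readings; only the last observation does not. SAP 6.7 says that double-blind exposure will not be presented for individual dose levels. The number of 30 mg/kg infusions is a listed variable and might give an approximate denominator for that one column.

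**Conclusion.** The point holds as a comparability problem between columns of unequal length. With identical risk per reading, whole-period placebo is expected to show a higher percentage than any shorter dose column. At an assumed 1% the figures are 46.9% against 7.7% (2-week step) or 33.1% (30 mg/kg, Weeks 7-16) under independence, and 17.5% against 5.8% or 14.5% at an assumed ICC of 0.1. The direction follows from the schedule and the counting rule. The size rests on the assumed rate, the assumed correlation and a 16-week double-blind period, none of which the documents fix as a single value.

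It does not extend to placebo against any-dose casimersen over the same period, and near-100% incidence is only a possibility in the single-group Casimersen Period.

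**What to change.** In SAP 6.8.5:

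1. Beside each patient percentage, report flagged readings over readings taken for that column. This is the change that deals with unequal reading counts.
2. Tabulate treatment-emergent abnormalities as well as any-time abnormalities: criterion not met at baseline, or worsened from baseline, in line with the laboratory definition in SAP 5.8. State what counts as worsening for a patient already beyond a limit. This deals with pre-existing abnormalities; it does not by itself remove the effect of column length.
3. State that patient percentages are to be compared only between columns of equal duration (placebo against any-dose casimersen), or show placebo for the same week windows as each dose column.
4. Say which Section 5.1 columns the table will contain, and whether criteria are counted separately or as a composite.

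Showing pre- and post-infusion readings separately is optional.

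The cost is SAP wording and slightly longer tables. No new data and no change to study procedures are needed. Label: cheap improvement.

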### **Baseline**

Double-Blind Period (safety): Baseline will be defined as the last value prior to the first dose of study drug (casimersen or placebo) administration.

Casimersen Period (safety): Baseline will be defined as the last value prior to the first dose of casimersen administration.

Combined Double-Blind and Open-Label Period (efficacy): Baseline will be defined as the last value prior to the first dose of study drug (casimersen or placebo) administration.

CCI

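### The SAP plans no summary of vital-sign change from the same-visit pre-infusion reading, although the protocol collects the paired readings

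*SAP*

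**What the plan says.** **Collection.** Protocol 10.3.1 sets this timing whenever a dose is given: "vital signs are to be collected within approximately 30 minutes prior to the start of the infusion, and approximately 5, 30, and 60 minutes", the last three counted from the end of dosing. After 48 open-label weeks without an infusion reaction, sites may instead "collect vital signs prior to infusion and at 5 and 30 minutes post-infusion"; the schedule of events leaves this reduction to the investigator.

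**Baseline.** SAP 5.8 sets one reference value per period. The first rule reads: "Double-Blind Period (safety): Baseline will be defined as the last value prior to the first dose of study drug (casimersen or placebo) administration". In the Casimersen Period the reference is instead the latest reading before a patient's own first casimersen infusion. For the four patients who start on placebo, that is a value from the start of open-label treatment, not Week 1.

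**Change summaries.** SAP 6.8.5 states: "Baseline value, highest/largest absolute change and last observation and the corresponding change from Baseline will be summarized by analysis period and treatment group". The extreme depends on the parameter: "The largest absolute change from Baseline will be summarized for systolic blood pressure, diastolic blood pressure, and respiratory rate", while pulse and temperature use the highest value only. Results count only if they fall within 28 days of the last dose or before a new study drug is started.

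**Other outputs.** SAP 6.8.5 counts patients and abnormalities beyond the Appendix Table 4 limits at any post-baseline time, and lists vital signs. SAP 6.8.2 summarises adverse events within 24 hours of the start of an infusion as infusion-related reactions, with a separate adjudicated summary.

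No visible text plans a change from the same visit's pre-infusion value, or a summary by minutes after infusion.

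**The concern.** A reading before and several readings soon after each infusion form a repeated paired design, with each patient as his own control on the day. The difference within a visit removes visit-to-visit variation, which is valuable in a first-in-human intravenous study with only four placebo patients.

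The planned change table gives this up. It searches all post-baseline readings for one extreme. That extreme is governed mainly by how variable the readings are and how many there are. For pulse and temperature only the highest value is kept, so an acute fall appears only if it crosses a lower limit in Appendix Table 4 or happens to be the last observation.

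At stake is a consistent but moderate infusion-time shift. It could be present at nearly every casimersen infusion and still not stand out in any planned summary table.

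**Working it through.** The plan states no power, precision or vital-sign standard deviation, so there is no figure of its own to reproduce. The check has three parts.

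**1. Readings searched for the extreme** (four per visit, no missed visit, less the baseline reading)
- 12 double-blind visits: 12 × 4 − 1 = 47.
- 16 double-blind visits: 16 × 4 − 1 = 63.
- Casimersen-first patient, 144 weeks, all readings kept: 144 × 4 − 1 = 575.
- The same patient, open label from Week 17 and the 60-minute reading dropped after 48 open-label weeks: 64 × 4 + 80 × 3 − 1 = 495.
- Placebo-first patient, 128 open-label weeks with the same reduction: 48 × 4 + 80 × 3 − 1 = 431.

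**2. What the other outputs would catch**
- *Thresholds.* Appendix Table 4 limits are absolute, except for weight. A systolic fall from 115 to 90 mmHg meets no criterion, because the lower limit is 80.
- *Infusion-related reactions.* These are reported adverse events. Under Protocol 11.2.1 a test abnormality is an adverse event when it alters medical care, so a symptomless shift may never be reported.
- *Listings.* They hold the data, but a reader would have to pair several hundred readings per patient by hand.

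**3. Illustrative size, systolic pressure**

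From the documents: 8 versus 4 patients, one pre- and three post-infusion readings, and about 16 blinded weeks for the last patient enrolled. Assumed: a constant 6 mmHg fall at every post-infusion reading on casimersen; visit-to-visit SD and reading SD of 6 and 5 mmHg, ranging from 4 and 3 to 10 and 7.

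*Mean same-visit change* (average of three post-infusion readings minus the pre-infusion reading, averaged over visits). The visit effect cancels:

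SE = √[ s² × (1 + 1/3) / 16 × (1/8 + 1/4) ], where s is the reading SD.

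- s = 3: √(9 × 1.333 / 16 × 0.375) = 0.53; 6 / 0.53 = 11.3
- s = 5: √(25 × 1.333 / 16 × 0.375) = 0.88; 6 / 0.88 = 6.8
- s = 7: √(49 × 1.333 / 16 × 0.375) = 1.24; 6 / 1.24 = 4.8

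*Planned statistic* (signed largest absolute change from baseline, one per patient), by simulation:
- SDs 6 and 5: mean arm difference about −11 to −12 mmHg, sampling SD about 15, ratio about 0.7 to 0.8.
- Across the SD range: ratio about 0.5 to 1.1. Read as an unsigned size, about 0.2 to 1.2.
- With no drug effect and SDs 6 and 5, the statistic still averages about 24 mmHg over 16 visits and 30 mmHg over 144.

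A second simulation used other assumptions: 12 visits, a 10 mmHg fall at 5 and 30 minutes only, SDs from 6 and 4 to 10 and 6. The mean change to 5 minutes gave 6.7 to 10.0 standard errors, against 0.7 to 1.4 for the unsigned largest change. With a 5 mmHg fall the figures were 3.3 to 5.0 against 0.2 to 0.4.

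*One dose level.* The 4, 10 and 20 mg/kg steps have two visits each. Replacing 16 by 2 in the formula gives SE 1.5, 2.5 and 3.5 mmHg for s = 3, 5 and 7, so ratios of 4.0, 2.4 and 1.7. The gain is smaller there.

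**The case against.** The strongest reply is that the plan already delivers its endpoint. Protocol 7.3 asks for the incidence of vital-sign abnormalities. The threshold table gives that incidence by period and treatment group, needs no baseline for blood pressure, pulse, respiration or temperature, and admits post-infusion readings. Infusion safety is also covered through the infusion-related reaction summaries. All this stands: the gap is in the supplementary change table, not in the endpoint.

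A reader might infer more than the documents support:
- *That every reading is compared only with Week 1.* Only the extreme and the last value become changes, and the Casimersen Period baseline of placebo-first patients is later.
- *That growth obscures the comparison.* At an assumed 1.5 mmHg per year, drift is about 0.3 to 0.5 mmHg over 12 to 16 placebo-controlled weeks. It reaches about 4 mmHg only over 144 weeks, in the period without a comparator.
- *That the last observation is a post-infusion reading for long-term extension entrants and a non-infusion reading for everyone else.* Entrants have no follow-up visit, so theirs is normally post-infusion. For others the follow-up falls about 4 weeks after the last infusion, and the 28-day rule may include or exclude it.

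The simulation is also open to fair criticism. Its SDs and effect are assumed, the fall is constant from the first 4 mg/kg infusion although doses escalate, only blood pressure is modelled, and the paired mean suits that effect. Safety analyses are descriptive, so an arm contrast is not a planned criterion. The figures therefore show direction and rough size only.

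Finally, a paired table can repeat the extreme-value problem. With SDs 6 and 5 and no drug effect, the largest same-visit fall averages about 15 mmHg over 16 visits and 21 over 144. Hence the mean should lead.

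**Conclusion.** The point holds as an omission worth correcting. The protocol collects paired pre- and post-infusion vital signs, and no visible SAP text summarises the paired change. The threshold counts, adverse-event summaries and listings do not replace it for a consistent acute shift that stays within the absolute limits and goes unreported as an adverse event.

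Under the assumed SDs and a constant 6 mmHg fall, the planned statistic carries the signal at about 0.5 to 1.1 times its noise, and the mean same-visit change at about 5 to 11 times. The ranking follows from the design, because pairing removes the visit effect and a mean is less variable than an extreme. The exact ratios do not: responses that differ between patients or appear only at higher doses would lower the paired figure.

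This does not mean that the primary endpoint goes unanalysed or that infusion reactions are ignored.

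**What to change.** Add to SAP 6.8.5 a descriptive table, for each infusion-related vital sign, of post-infusion minus same-visit pre-infusion value at each nominal time (5, 30 and 60 minutes).

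- **Main summary:** the per-patient mean change, by placebo and casimersen dose level in the Double-Blind Period and overall in the Casimersen Period.
- **Counts:** show n at each time, and note that 60-minute data are selective once the permitted reduction applies, because only reaction-free patients qualify for it.
- **Extremes:** any largest rise or largest fall is supplementary and, in the Double-Blind Period, should be read against placebo.
- **Last observation:** use pre-infusion or non-infusion readings for its change from Baseline, subject to the existing 28-day rule.
- **Unchanged:** keep the Appendix Table 4 threshold table as planned.

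The cost is SAP wording and one more table per parameter. No new data and no change to trial procedures are needed.

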## 5. GENERAL STATISTICAL METHODS AND CONVENTIONS

### 5.1. General Methods

For continuous variables, descriptive statistics will include the number of patients with data to be summarized (n), mean, standard deviation (SD), median, minimum, and maximum.

For categorical/qualitative variables, descriptive statistics will include frequency counts and percentages. The total number of patients in a treatment group will be used as the denominator for percentage calculations, unless stated otherwise.

Unless stated otherwise, summaries of all endpoints will be by treatment group (see below for definitions of treatment groups) for 3 "Analysis Periods" (Double-Blind Period, Casimersen Period and Combined Double-Blind and Open-Label Periods):

Double-Blind Period: Data will include all assessments and events that occurred prior to the first dose of 30 mg/kg of casimersen in the open-label period. The analyses for the double-blind period will be primarily for safety.

Double-blind Period analysis treatment groups are:

- patients who received placebo during the double-blind Period
- patients who received casimersen at 4 mg/kg (Weeks 1-2), 10 mg/kg (Weeks 3-4), 20mg/kg (Weeks 5-6), and 30mg/kg (Weeks 7-8)
- <=20 mg/kg during Week 1 to 6 (only used for select endpoints)
- patients who received casimersen at 30 mg/kg during Weeks 7 to the end of the double-blind period
- patients who received casimersen at any dose level during Weeks 1 to the end of the double-blind period

Casimersen Period: For AEs and other safety-related data analysis, data will include all assessments and events that occurred while patients received casimersen. Assessments and events that occurred in the double-blind period for patients who were on placebo during the double-blind period will be excluded. Assessments and events that occurred during the double-blind period for patients who received casimersen will be included.

Casimersen Period Analysis treatment group is:

- all casimersen treated patients: Patients who receive casimersen in any portion of the study

Combined Double-blind and Open-label Periods: For efficacy data analysis, data will include all assessments and events during both treatment periods of the study.

Combined Double-blind and Open-label Periods Analysis treatment groups are:

- Placebo-Casimersen: Patients who receive placebo in the double-blind period followed by casimersen in the open-label period

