#### **6.8.6.      Electrocardiograms and Echocardiogram**

The frequency and percentage of patients with values meeting the potentially clinically significant abnormality criteria (defined in [Appendix Table 5](#)) at any time point will be summarized by Analysis Period and treatment group as defined in Section [5.1](#) for both ECGs and ECHOs. The number of potentially clinically significant abnormalities will also be presented.

Baseline value, highest/largest absolute change/largest change (ECGs only) and last observation and the corresponding change from Baseline will be summarized by treatment group. The largest change will be summarized for QTcF, QRS and PR intervals, the highest value for QT and largest absolute change for heart rate. If the largest absolute change from Baseline is occurs in both directions equally then the higher value will be summarized. Only results that occurred within 28 days of the last dose of study drug, or before initiation of a new study drug will be included.

All patient-level values for ECG and ECHO variables will be displayed in a data listing. In addition, values meeting the potentially clinically significant criteria will be presented in a data listing. Treatment-emergent abnormalities will be indicated.

CCI

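### Blood pressure, respiratory rate and ECG heart rate are summarised by one largest absolute change per patient, which mixes rises with falls in the mean and median and drops each patient's opposite extreme

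*SAP*

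**What the plan says.** For vital signs, SAP 6.8.5 sets out the continuous summaries as follows: "Baseline value, highest/largest absolute change and last observation and the corresponding change from Baseline will be summarized by analysis period and treatment group". It then assigns a statistic to each parameter. "The largest absolute change from Baseline will be summarized for systolic blood pressure, diastolic blood pressure, and respiratory rate"; pulse and temperature get the highest value only. If a patient's largest change is equal in "both directions equally, then the higher value will be summarized". SAP 6.8.6 uses "the highest value for QT and largest absolute change for heart rate" and repeats the tie rule.

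SAP 5.1 summarises continuous variables by n, "mean, standard deviation (SD), median, minimum, and maximum". Separately, SAP 6.8.5 reports "The frequency and percentage of patients meeting any of the potentially clinically significant abnormality criteria" of Appendix Table 4, which has both a lower and an upper limit for blood pressure, pulse, respiratory rate and temperature. All vital signs are listed by patient.

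SAP 6.8.4 handles laboratory tests differently. Where a test can move either way (for example potassium, sodium or glucose), the highest and lowest values are each summarised, and there is a shift table for each direction.

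**The concern.** These parameters can move in either direction, and Appendix Table 4 treats the vital signs among them that way. A statistic that keeps only the reading furthest from baseline, whichever way it went, answers neither how far patients rose nor how far they fell. If the sign is kept, opposite movements offset each other in the two statistics that readers look at first. If it is dropped, rises and falls cannot be told apart. In both cases a patient with a large rise and a slightly smaller fall contributes only the rise.

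Safety is the primary objective of this first-in-human trial, and the arms have 8 and 4 patients. The descriptive tables should therefore show direction clearly, and the SAP already has a format that does so.

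**Working it through.** The plan gives no figure on this point, so there is none to reproduce. Inputs from the documents:
- Arms of 8 and 4 (SAP 4.2).
- Appendix Table 4 limits: systolic <80 or >130, diastolic <40 or >90, respiratory rate <12 or >20, pulse <50 or >130, temperature <36.0 or >38.0.
- Appendix Table 5, ECG heart rate: normal limits 50 and 120, markedly abnormal criterion NA.
- Four vital-sign readings per infusion visit, one before and three after (Protocol Table 2, vital signs footnote).

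1. *Is the sign kept?* If only the magnitude were tabulated, +25 and -25 would both be 25 and there would be no tie to break. A rule that "then the higher value will be summarized" has a purpose only if the reading itself or the signed change is reported. The reading at the selected time mixes high and low values whatever is done with the sign of the change.

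2. *Effect on the mean and median.* With k of n patients at +a and n-k at -b, the signed mean is [k·a - (n-k)·b]/n, which is zero when k·a = (n-k)·b.
 - n = 8, k = 4, a = b = 25: mean (100 - 100)/8 = 0, median 0, SD √(8 × 25²/7) = 26.7, minimum -25, maximum +25.
 - n = 4, k = 2: mean 0, median 0, SD √(4 × 25²/3) = 28.9.
 - Unsigned, every patient scores 25, exactly as if all had risen.

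3. *Do the limit counts show it?* The systolic window is 130 - 80 = 50 mmHg wide. From a baseline of 105, a change of ±25 reaches 130 or 80, and neither is beyond the limit. One patient going from 125 to 85 and another from 85 to 125 give -40 and +40: mean 0 and no count. A patient with both +30 and -30 spans 60 mmHg and must cross a limit: above 130 if baseline exceeds 100, below 80 if baseline is under 110. The diastolic window is also 50 mmHg wide, with 60 and 70 as the corresponding baselines. The counts therefore catch large two-way swings but not every sizeable change.

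4. *The discarded extreme.* If all eight patients, from a systolic baseline of 105, had both +25 and -25, the tie rule would select the rise each time. The row would read mean +25, SD 0, minimum +25. The falls would appear neither in that row nor in the counts. Exact ties are plausible for respiratory rate, which is counted over one minute (Protocol 10.3.1).

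5. *Illustrative simulation.* Assumptions not in the documents: independent normal readings, within-patient SD 8 units, one baseline reading, 48 later readings (taken as 12 weekly infusions × 4), shifts of 20 units on a quarter of readings, n = 8, 4,000 repetitions. Entries are averages over repetitions.

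| Scenario | Signed mean | SD | Min / max | Mean largest rise / fall |
|---|---|---|---|---|
| No effect | -0.1 | 25.1 | -30.5 / +30.4 | +17.8 / -17.9 |
| Four patients +20, four -20 | 0.2 | 36.4 | -42.7 / +42.6 | +25.0 / -25.0 |
| Every patient has both | 0.0 | 37.4 | -43.5 / +43.5 | +30.2 / -30.2 |

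For the second scenario, with assumed SDs of 6 to 10, the signed mean stays at 0.1 to 0.2. The group SD rises from 18.7 to 32.3 at SD 6 and from 31.3 to 40.9 at SD 10. So the mean does not move, the SD, minimum and maximum do, and separate rows show the effect directly.

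**The case against.** A reader might infer that the table can show no effect when rises and falls both occur. The documents do not support that. SAP 5.1 puts SD, minimum and maximum in the same summary, and step 5 shows that they widen. The two-sided counts catch a ±30 mmHg swing from any baseline. Last observations are also summarised, and with 12 patients the listings can be read in full.

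A reader might also infer that falls in pulse and temperature go unsummarised. They do not: pulse below 50 and temperature below 36.0 are counted. Only a lowest-value row is missing.

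Nor is the primary endpoint at risk. Protocol 7.3 words it as incidence of abnormalities in vital signs and clinically significant worsening of ECGs; SAP 4.4.1 also refers to incidence. Neither document makes the largest-change mean a formal comparison. That the sign is kept is an inference, since the SAP never says so. The simulation does not fit ECG heart rate, which in the titration schedule is recorded after baseline only at Weeks 7 and 12.

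These points stand and limit the weight of the finding. They do not make the statistic a good one. Even with no effect, the simulated minimum and maximum are about -30 and +30, so in arms this small a wider spread is hard to separate from noise. The counts miss changes inside the limits. ECG heart rate has no markedly abnormal criterion; its normal limits of 50 and 120 are printed, but the SAP does not say that they serve as one. Vital-sign pulse gives some cover, but through other readings.

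**Conclusion.** The point holds as a weakness in a supportive descriptive table. If the sign is kept, as the tie rule implies, the mean and median are uninformative for mixed-direction changes and can sit at or near zero. Whether or not it is kept, each patient's extreme in the other direction is discarded. The other planned outputs partly compensate. The gap is widest for ECG heart rate and for blood pressure or respiratory rate changes that stay inside the Appendix Table 4 limits.

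The zero mean in step 2 is arithmetic and needs only the signed reading. The simulated sizes depend on assumed variability, independence and shifts, and are illustrative only. No hypothesis test, sample size or stopping rule is affected.

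**What to change.** In SAP 6.8.5 (systolic and diastolic blood pressure, respiratory rate) and 6.8.6 (ECG heart rate), replace the largest absolute change with two rows: largest increase and largest decrease from Baseline, each with its value. This follows the highest and lowest format of SAP 6.8.4. Add the lowest value for pulse and temperature beside the highest. Delete the tie rule in both sections, since it then has nothing to decide.

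The cost is SAP wording and one extra row for each of six parameters, with no new data and no change to any other analysis. It is a free improvement, and should be made before the database is locked and unblinded for the final analysis (SAP 4.5.2).
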